**OBJECTIVES:**

Participants with chronic, refractory phantom limb pain (PLP) or residual limb pain (RLP) for more than 6 months will be enrolled in this clinical trial.

Aim: Define the attributable pain relief and functional improvement in participants with PLP/RLP after contralateral limb sciatic nerve block. Also, contribute to the basic science understanding of the crossed-withdraw reflex by demonstrating a known animal model phenomenon in human participants.

Hypothesis: Contralateral limb sciatic nerve anesthetic block with 2% lidocaine provides immediate clinically meaningful pain reduction, defined as the proportion of patients with at least 50% improvement in NRS pain score in PLP/RLP when compared to sham.

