### Secondary Outcomes (between and within-group comparisons will be used for each outcome):

- 1) Mean and standard deviation (SD) of change in NRS pain score at 1, 2, 3, 4, 5, 6, 24, 48, 72, 96, 120 hours post-saline and lidocaine injections
- 2) Mean and SD of average daily steps recorded at 24, 48, 72, 96, 120 hours post-saline and lidocaine injections (via Modus StepWatchTM or Evolution EvoWalkTM)

STU#:

- 3) Mean and SD of change in Orthotics and Prosthetics User's Survey (OPUS) score immediately post-injection and conclusion of washout (5 days) in saline and lidocaine groups
- 4) Mean and SD of change in Groningen Activity Restriction Scale (GARS) score immediately post-injection and conclusion of washout (5 days) in saline and lidocaine groups
- 5) General linear model analysis of the interaction between crossover sequence
- 6) Demographic factors associated with large improvement in NRS pain score
- 7) Complications associated with the procedures

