Treatment block of sciatic nerve in contralateral limb: Procedure planning will be based on the participant’s indication of residual limb point of maximal pain (measured by distance from posterior superior iliac spine (PSIS) to most painful point [in cm]). Note that this point may beyond the anatomic end of the residual limb. The block will be performed at the exact same distance from PSIS on the contralateral side. If the block cannot be performed at this site due to anatomic or technical considerations (such as proximity to vascular structures), a more cephalad site along the sciatic nerve course will be selected for the procedure. During the block procedure, the participant will be positioned prone. Standard American Society of Anesthesiologists (ASA) procedure monitoring will be used (pulse oximetry, ECG, blood pressure, and heart rate). The participant’s skin will be prepared with chlorhexidine. A sterile ultrasound probe will be placed on the participants’ residual limb at a transverse angle in order to view the nerve in short-axis. The skin will be anesthetized with 1-2 mL of 1.0% lidocaine. The ultrasound probe (in plane) will be advanced to the intact limb’s sciatic nerve equidistance to that of the residual limb point of maximal pain. A 22-gauge standard echogenic needle will be placed adjacent to the sciatic nerve with ultrasound guidance. At the site of the nerve, 10mL of 2% lidocaine will be injected through the needle in the intervention group and 10ml of saline will be injected in the sham group.

In treatment group: At the site of the nerve, 10mL of 2% lidocaine will be injected through the needle

In control group: At the site of the nerve, 10ml of saline will be injected through the needle

Following injection, participants will be kept in recovery area and monitored for 30 minutes. They will also complete a pain log starting 15 minutes post-injection. After the first pain score is recorded, the participants will dress and exit procedure area. Participants will be required to arrange transportation as the block may impair lower extremity motor function.

Both saline and local anesthetic will be administered to all subjects with a crossover design as described above. Participants will undergo 5-day washout between injections.

*Visit 3 – Crossover for both groups*

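### OPUS and GARS scored immediately after injection cannot show functional improvement and do not appear in the visit schedule; first-24-hour steps should be read as a net effect of the block

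*Combined protocol and SAP*

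**What the plan says.** The aim under Objectives is to "Define the attributable pain relief and functional improvement in participants with PLP/RLP after contralateral limb sciatic nerve block". The Visit 2 section places the injection on the sound leg: the probe "will be advanced to the intact limb’s sciatic nerve equidistance to that of the residual limb point of maximal pain". It gives the two conditions as "10mL of 2% lidocaine will be injected through the needle in the intervention group and 10ml of saline will be injected in the sham group". It also expects a possible motor effect: "Participants will be required to arrange transportation as the block may impair lower extremity motor function".

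Three secondary outcomes concern function:

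- Item 2: "Mean and SD of average daily steps recorded at 24, 48, 72, 96, 120 hours post-saline and lidocaine injections".
- Item 3: change in OPUS, right after injection and at the end of the 5-day washout. The Data section specifies the lower-extremity functional status subsection.
- Item 4: change in "Groningen Activity Restriction Scale (GARS) score immediately post-injection and conclusion of washout (5 days) in saline and lidocaine groups".

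The Devices section leaves the step counter on the prosthesis until the study ends, so the hours just after injection are counted. The Data section lists no measure of motor strength. The Statistical Plan neither sets the block period apart nor adjusts for weakness.

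**The concern.** Two of the three functional outcomes have a time point at which function in daily life cannot be observed. A participant answering OPUS or GARS immediately after the injection is still in the recovery area and has not resumed ordinary activity. In the lidocaine period the intact leg may also be weak or numb. A lidocaine-saline difference at that point could be published as evidence on function when it is not. The first 24-hour step count raises a milder form of the same question, because it adds any gain from pain relief to any loss from weakness, and nothing that is collected separates them. What is at stake is how the functional part of the aim is interpreted, not the primary result.

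**Working it through.** **The plan's own figure.** The documents give no expected effect, variance or power for function. The one sample-size figure, N = 20, belongs to the primary outcome. From the Power Analysis, the discordant proportions are (0.875 + 0.625)/2 = 0.750 and (0.875 − 0.625)/2 = 0.125. Exact two-sided McNemar power at alpha 0.05 is 0.790 with 17 pairs and 0.830 with 18. Allowing 10% dropout, 18/0.90 = 20. The figure reproduces and is not touched by this point.

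**Outcome list against visit schedule.**

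| Measure | Secondary Outcomes | Visit sections |
|---|---|---|
| OPUS | immediately after injection; 5 days | Visit 1; before procedure 2; telephone at days 1 and 5 |
| GARS | immediately after injection; 5 days | Visit 1 only |

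After the injection, the Visit 2 section describes 30 minutes of monitoring and a pain log starting at 15 minutes, but no questionnaire. The immediate OPUS and GARS scores therefore exist only in the outcome list. For GARS, neither listed post-injection point has a scheduled collection.

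**What an immediate score could mean.** The documents give no recall period for either instrument, so there are two cases.

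1. If participants rate their usual function, the answer cannot yet reflect the injection, and the change should be near zero in both periods.
2. If they rate function at that moment, the lidocaine answer may reflect a weak leg, which pulls it down. A numb leg may also reveal the assignment, which could push a self-report up.

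In neither case does the score measure functional improvement after the block, and the direction of error cannot be settled from the documents.

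**Steps in the first 24 hours.** Block duration is not stated. The following is an illustration that assumes no steps during a block of h hours and an even step rate over w waking hours in the window, with h from 1 to 4 and w from 8 to 16.

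- Share of first-day steps lost = h/w: 1/16 = 6%; 2/12 = 17%; 4/8 = 50%.
- Rise in step rate over the rest of that day needed to break even = (h/w)/(1 − h/w): 7%, 20% and 100% for the same three cases.
- Under these assumptions the separate 24-hour windows ending at 48, 72, 96 and 120 hours lose nothing. If the later values were instead running averages from injection, the loss would carry forward diluted: at 120 hours, 6%/5 to 50%/5, or about 1% to 10%. The outcome wording does not say which is meant.

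**Overlap with procedure 2.** The Visit 2 section states a 5-day washout, while the Visit 3 section has participants return within 5 days of visit 2. If visit 3 falls before 120 hours, the last window for the first injection would include time after the second.

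**The case against.** The strongest reply is that Objectives and Background ask for effects of the block, not of pain relief alone. On that wording weakness is part of the effect, and the randomised first-day step difference is a valid net effect. This stands. So does the observation that the 48- to 120-hour step values are already listed as separate time points, so data outside the assumed block period are already planned. It can also be said that if the visit schedule is followed, OPUS will be taken at day 1, when overlap with the block may be small. That stands too, but it means the outcome list has to be corrected to match.

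A reader might infer something stronger: that the functional outcomes as a whole are biased against lidocaine, so that the functional aim would be answered wrongly. The documents do not support that. The target they state is the effect of the block; the direction for OPUS and GARS is open; most step time points lie outside the assumed block period; and no block duration or expected functional gain is given against which to call a gain hidden. Nor does it follow that the first day should be dropped from the step outcome. The hypothesis concerns immediate relief, so that is the day on which a benefit would be expected.

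**Conclusion.** The point holds for the immediate OPUS and GARS scores. They cannot show functional improvement after the block, and they conflict with a schedule that collects no questionnaire at that time and no GARS at all after visit 1. For steps, what remains is a matter of labelling: the first-24-hour difference is a net effect that includes any motor weakness and should not be read alone as evidence for or against functional benefit. The range of about 6% to 50% of first-day steps rests wholly on the assumed 1 to 4 hours of block, 8 to 16 waking hours, no walking during the block and an even step rate otherwise; the documents supply none of these. Only secondary outcomes are involved: one of two time points for each questionnaire and one of five for steps. This is a low-cost improvement, not a threat to the trial's main conclusion.

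**What to change.** - In secondary outcomes 3 and 4, replace the immediate time point with the day-1 telephone call, which already collects OPUS, and keep the 5-day point.
- Add GARS to the day-1 and day-5 calls. The Visit 3 section numbers three calls, which would fit two day-1 calls and one day-5 call, with visit 3 standing in for the other. If that is the intent, add GARS to the collection before procedure 2 as well.
- Reconcile the outcome list with the Visit 1, 2 and 3 sections so that each listed score has a scheduled collection, and reconcile the two statements on the interval between procedures.
- For steps, keep all five time points and state that each covers its own 24-hour window. Report the first as the net effect of the block including any motor weakness, and interpret it beside the 48- to 120-hour values. For the first injection, count only time before procedure 2.

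The cost is a rewording of items 2 to 4 and a few extra minutes on contacts already planned. No visit is added and the sample size does not change. The downside is that a functional change lasting only hours on the injection day would not be captured by OPUS or GARS.

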### *Devices*

During initial evaluation (visit 1), participants' prostheses will be fit with a Modus StepWatch™ or Evolution EvoWalk™. This will be tested in clinic by a research coordinator to ensure proper step count. The device will remain on participant's prosthesis until study completion. Participant kinematic and gait data will be recorded by Modus StepWatch™ or Evolution EvoWalk™ and uploaded via Bluetooth to secure a de-identified, Health Insurance Portability and Accountability Act (HIPAA) compliant cloud-based storage application and extracted by research coordinator to an encrypted, HIPAA-compliant, Northwestern research database (REDCap).

Participants will also be instructed to maintain a daily pain log through My Pain Diary smartphone application or paper log depending on participant preference. They will be asked to log daily pain scores during their treatment. Data will be extracted by a researcher to an encrypted, HIPAA-compliant, Northwestern research database (REDCap).

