### *Visit 2 (procedure 1)– Randomization and Study Intervention*

STU#:

Eligible participants will return to the Lavin 14th floor Pain clinic within 2 weeks of the initial visit. Participants will be randomized to treatment or sham group. Participant pre-procedure 1 NRS pain score will be collected. Individual pain log will start 15 minutes after procedure. Participant will log pain score every hour until asleep. The next day, participant will record daily NRS pain score for 5 days.

Randomization

A computer-generated 1:1 block randomization scheme (<https://www.randomizer.org>) will be used to assign participants to receive a peri-sciatic nerve injection with either 10 mL of 2% lidocaine or 10 mL of preservative-free saline (compounded by the 11th floor Lavin pharmacy and labeled with a “1” or “2” to ensure adequate blinding). Randomization will be performed by a research assistant by opening an opaque envelope to reveal the participant number and group assignment printed inside of the envelope. This will instruct authorized study personnel to draw up either 2% lidocaine or saline (labeled “1” or “2” by compounding pharmacy per above). The blinded injectionist will be provided an unlabeled syringe of injectate immediately before the injection procedure. Participants, injectionist, and study personnel who collect outcomes data will be blinded to group assignment.

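### The step outcome has no pre-injection reference, although the counter is worn from Visit 1, so the promised within-group comparison cannot show change from usual walking

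*Combined protocol and SAP*

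**What the plan says.** The Secondary Outcomes section of the combined protocol and SAP heads its list with the statement that "between and within-group comparisons will be used for each outcome". The items that follow are not defined alike:

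- Outcome 1 (pain) is a change score: "change in NRS pain score at 1, 2, 3, 4, 5, 6, 24, 48, 72, 96, 120 hours". Outcomes 3 (OPUS) and 4 (GARS) are also defined as change.
- Outcome 2 (steps) is a level: "Mean and SD of average daily steps recorded at 24, 48, 72, 96, 120 hours" after each injection.

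Under Devices, the participants' "prostheses will be fit with a Modus StepWatch" or an alternative counter at Visit 1, and "The device will remain on participant's prosthesis until study completion". Procedure 1 takes place at Visit 2, "within 2 weeks of the initial visit"; no minimum interval is given.

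No section defines a baseline step count. The Visit 1 text mentions baseline outcome measures in general terms, but the counter is only fitted at that visit. The variable list under Data contains no step variable. For normally distributed continuous variables the Statistical Plan specifies an unpaired t test, and otherwise a Mann-Whitney U test.

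**The concern.** A within-group comparison of a functional measure is naturally read as after against before, within one condition. For steps the plan supplies only the after. Two kinds of comparison remain: one post-injection day against another, and lidocaine against saline. Neither shows whether participants walked more or less than they usually do. A positive lidocaine-saline difference would fit more walking than usual after lidocaine, but it would equally fit less walking than usual after both injections with a smaller drop after lidocaine.

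The stated aim includes functional improvement, and steps are the only functional outcome recorded by a device. The pre-injection recordings that would settle the direction will normally exist, but they are given no role.

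**Working it through.** **1. What the design makes available.**

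| Interval | Steps recorded? | Free of both injections? | Used in the plan? |
|---|---|---|---|
| Visit 1 to procedure 1 (up to 14 days, no minimum) | Yes | Yes | No |
| 24 to 120 h after procedure 1 | Yes | No | Yes, as a level |
| 24 to 120 h after procedure 2 | Yes | No | Yes, as a level |

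The period 1 outcome window runs to 120 h, and 120/24 = 5 days. The washout is also 5 days, so the days before procedure 2 are the period 1 outcome days. Period 2 has no clean baseline of its own, and the run-in is the only step record that neither injection can affect.

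**2. The plan's own figure.** The documents give no sample size, SD or correlation for steps. The total of 20 belongs to the primary outcome and reproduces. The discordant probabilities are (0.875 + 0.625)/2 = 0.75 and (0.875 − 0.625)/2 = 0.125. An exact two-sided McNemar test has power 0.790 with 17 pairs and 0.830 with 18, and 18/0.9 = 20. Nothing below changes that number. The 18 completers are carried forward.

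**3. Effect of a baseline on the precision of the lidocaine-saline step difference.** Assumptions: SD 1 for each of baseline B, lidocaine L and saline S; one common correlation ρ between them; n = 18.

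- Unpaired test, no baseline: variance 2/n = 2/18 = 0.111.
- Unpaired with baseline as covariate: 2(1 − ρ²)/n, a cut of ρ².
- Unpaired on change from baseline: 4(1 − ρ)/n, a cut of 2ρ − 1, which is negative when ρ is below 0.5.
- Paired, no baseline: 2(1 − ρ)/n, a cut of ρ.
- Paired, with the run-in baseline subtracted: (L − B) − (S − B) = L − S, so nothing changes.

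| ρ (assumed) | Unpaired | Covariate (cut) | Unpaired change score (cut) | Paired (cut) |
|---|---|---|---|---|
| 0.3 | 0.111 | 0.101 (9%) | 0.156 (40% worse) | 0.078 (30%) |
| 0.5 | 0.111 | 0.083 (25%) | 0.111 (0%) | 0.056 (50%) |
| 0.7 | 0.111 | 0.057 (49%) | 0.067 (40%) | 0.033 (70%) |
| 0.9 | 0.111 | 0.021 (81%) | 0.022 (80%) | 0.011 (90%) |

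A simulation with 20,000 replicates at ρ of 0.5, 0.7 and 0.9 gave identical paired estimates with and without the baseline. For a difference of 0.5 SD (assumed) at ρ = 0.7, simulated power was 0.21 unpaired, 0.46 unpaired on change and 0.73 paired without a baseline.

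**4. Period 1 alone.** If only period 1 could be used, about 18/2 = 9 participants per arm would be compared and pairing would be unavailable. The unadjusted variance would be 2/9 = 0.222. The proportional cuts from covariate adjustment are the same ρ² as above.

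**The case against.** The strongest reply is that this is a crossover and each participant is their own control. The aim concerns attributable improvement, which is a contrast with sham and needs no run-in. This stands for the treatment contrast. A reader might infer that ignoring the run-in wastes precision throughout, perhaps citing a standard error reduction of 29% to 56% (1 − √0.51 and 1 − √0.19, at ρ of 0.7 and 0.9). The documents do not support that. The figure applies only to covariate adjustment in an unpaired or period 1 comparison, and only at favourable correlations that the documents do not give. With complete data the same people supply both condition means, so stable differences between people cancel from the estimate. What they inflate is the standard error of the unpaired test, and pairing repairs that better at every ρ in the table.

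A reader might also infer that the within-group comparison has nothing at all to work with, or that the functional aim fails. Both go too far. Five post-injection days can be compared with one another, and the saline period is a within-person reference. OPUS and GARS also measure function, are defined as change and are collected at Visit 1. What is missing is specifically the before-to-after reference for steps.

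Finally, a usable baseline cannot be taken for granted. Visit 2 has only an upper limit on timing, so some participants could have few or no full wear days. This stands, and the fix has to deal with it.

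**Conclusion.** The point holds as a small, inexpensive improvement. The step outcome is the only one of the four measured outcomes not defined as change, the plan promises a within-group comparison for it, and pre-injection steps that could serve as the reference are normally recorded but unused. The consequence is interpretive: as written, the step data cannot show change from usual walking.

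On precision, the gain from the baseline is zero in a fully paired contrast. Under the unpaired test as written it is about 9% to 81% of the variance for ρ from 0.3 to 0.9, less than the 30% to 90% from pairing alone. These figures rest on assumed correlations, equal variances, a common correlation and 18 completers. The interpretive conclusion rests on none of them.

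**What to change.** - Define baseline steps as mean daily steps over a stated minimum number of full wear days between Visit 1 and procedure 1. State what counts as a full wear day, and add the variable to the list under Data.
- Use this baseline as the reference for within-group change after each injection. Report that change descriptively, since it has no control and in period 2 also carries any period effect.
- Estimate the lidocaine-saline step contrast within participant.
- In any unpaired or period 1 step comparison, enter the baseline as a covariate. Do not use an unpaired change score, which loses precision when ρ is below 0.5.
- State how participants without enough wear days are handled. They can stay in the paired contrast, which needs no baseline.

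The cost is SAP text, one derived variable and retention of recordings already planned. The downside is that participants whose Visit 2 follows soon after Visit 1 would have no baseline. Avoiding that would need a minimum interval between the two visits, which is a scheduling change and not only a change of wording.

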Eligible participants will return to the Lavin 14th floor Pain clinic within 5 days of visit 2. Participant pre-procedure 2 NRS and OPUS will be collected. Note that this will serve as post-procedure 1 washout and pre-procedure 2 intervention data point.

Both groups: will cross over and undergo treatment as described in *Visit 2*. Participant pain log will start 15 minutes after procedure 2. Participant will log pain scores every hour until asleep. The next day, participant will record daily NRS pain score for 5 days.

*Telephone call 1,2,3:* participant will be called at 1- and 5-days post-procedures for NRS, OPUS survey and safety monitoring by research coordinator (see Safety Monitoring below).

**SAFETY MONITORING** Participants will be contacted one day following both interventions to assess for any adverse events or side effects.

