#### STATISTICAL PLAN

Data for the primary outcome variable, proportion of participants reporting  $\geq 50\%$  immediate pain reduction from baseline, will be reported as the mean and standard deviation (or median and interquartile range if not normally distributed) of the lidocaine and sham groups. Mean change in pain score, will be examined using an unpaired t test (NCSS) (or Mann-Whitney U test if not normally distributed). The median difference and its 95% CI will be calculated. The criterion for rejection of the null hypothesis will be  $P < 0.05$ .

Participant data and secondary variables that are characterized by nominal data will be summarized as the number of participants in each category and the percentage of all participants in the group that they represent. These variables will be compared between the groups using the Pearson  $\chi^2$  test, or when at least one of the cells of the contingency table had an expected number less than five, the Fischer exact probability test. The Miettinen-Nurminen score will be used to calculate 95% CIs for differences in percentages where indicated.

Variables that are characterized by ordinal data and non-normally distributed continuous data (e.g., procedure time) will be summarized as median and interquartile range. These variables will be compared between the groups using the Mann-Whitney U test. Median differences and their 95% CIs will be calculated where indicated.

Variables that are characterized by normally distributed continuous data (e.g., age and body weight) will be summarized as mean and standard deviation. These variables will be compared between the groups using the unpaired t test (NCSS). Mean differences and their 95% CIs will be determined.

In case there were significant differences in the demographic variables, multivariate logistic and linear regression analyzes will be conducted to examine the binary and continuous outcome variables by group, while accounting for the statistically significant demographic variables analysis will be used to determine if any demographic or clinical variables (age, BMI, duration of pain, etc.) are independently associated with successful pain (NRS) outcomes.

Lastly, Pearson's correlation coefficients will be computed to assess the relationships among various demographic and procedural covariates.

STU#:

STU#:

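### Daily steps would be compared with an unpaired test that ignores the crossover pairing and the day of the week, although matched step days never fall on the same weekday (minor, secondary endpoint only)

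*Combined protocol and SAP*

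**What the plan says.** Under Study Endpoints, Secondary Outcomes, item 2 is "Mean and SD of average daily steps recorded at 24, 48, 72, 96, 120 hours post-saline and lidocaine injections". The heading of that list adds that "between and within-group comparisons will be used for each outcome". Item 5 announces a general linear model on crossover sequence, with no calendar term.

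On timing, the Visit 2 text says "Participants will undergo 5-day washout between injections". The Visit 3 text says participants return "within 5 days of visit 2". The order of injections is set by "A computer-generated 1:1 block randomization scheme".

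The Statistical Plan does not name steps. They fall under its general rule for normally distributed continuous variables: "These variables will be compared between the groups using the unpaired t test (NCSS", or under the Mann-Whitney test if they are not normal. The only adjustment offered is regression "while accounting for the statistically significant demographic variables", and only if such differences are found.

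The Devices section has the step counter fitted at Visit 1 and left on the prosthesis until the study ends. Visit 2 follows within 2 weeks of Visit 1.

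**The concern.** Step count is the only device-recorded measure of the functional improvement named in the aim; OPUS and GARS are self-reported. People may walk different amounts on weekends and weekdays. If the step day after lidocaine is a Sunday and the matching day after saline is a Friday, that difference enters the participant's lidocaine-saline contrast.

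Its direction depends on the weekday of Visit 2 and on the order of injections, so a period or sequence term removes only part of it. With 20 enrolled and 10% dropout, about 18 pairs remain, and avoidable variance costs something. The plan neither pairs the two step totals of one person nor uses the date of each total, though the counter supplies both.

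**Working it through.** **Plan's own figure.** The Power Analysis covers only the primary outcome. A discordant proportion of 0.875 and a difference of 0.625 give cells of 0.75 and 0.125. Exact two-sided McNemar power at alpha 0.05 is 0.790 for 17 pairs and 0.830 for 18, so 18 pairs are needed; 18/0.90 = 20. The stated N reproduces. No figure is given for steps.

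**Same weekday?** Two step days share a weekday only if the gap is a multiple of 7. No gap of 1 to 5 days is.

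**Weekend against weekday, gap exactly 5 days, any start day allowed.** If the period-1 step day is Saturday, Sunday, Monday or Tuesday, the matching period-2 day is Thursday, Friday, Saturday or Sunday. That is 4 of 7 = 57% at every mark.

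**Same gap, both procedures Monday to Friday (assumption).** Only Wed/Mon, Thu/Tue and Fri/Wed are possible. Next-calendar-day totals, with +1 if only the period-1 day is a weekend day and -1 if only the period-2 day is:

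| Mark | Wed start | Thu start | Fri start | Share mismatched |
|---|---|---|---|---|
| 24 h | Thu/Tue, 0 | Fri/Wed, 0 | Sat/Thu, +1 | 33% |
| 48 h | Fri/Wed, 0 | Sat/Thu, +1 | Sun/Fri, +1 | 67% |
| 72 h | Sat/Thu, +1 | Sun/Fri, +1 | Mon/Sat, -1 | 100% |
| 96 h | Sun/Fri, +1 | Mon/Sat, -1 | Tue/Sun, -1 | 100% |
| 120 h | Mon/Sat, -1 | Tue/Sun, -1 | Wed/Mon, 0 | 67% |

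The shares take the three start days as equally used. With a gap of 3 or 4 days the 96 h share is 1 of 3, and the full mismatch moves to 48 and 120 h.

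**Variance of a paired single-day contrast.** Let s be the within-person daily SD and w·s the weekend effect. The paired difference has variance 2s². With randomised order the mismatch adds m·w²·s², where m is the share mismatched, so the inflation is m·w²/2. The documents give no w.

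| w (assumed) | m = 1: w²/2 | 96 h after period adjustment: (8/9)·w²/2 |
|---|---|---|
| 0.25 | 3.1% | 2.8% |
| 0.5 | 12.5% | 11.1% |
| 1 | 50% | 44.4% |

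The factor 8/9 is the variance of +1, -1, -1, that is 1 - (1/3)². Period adjustment leaves most of the swing because its sign changes with the start day.

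**Unpaired test.** Let rho be the share of step variance that lies between people. Each observation has variance s²/(1 - rho). With m = 1, each treatment's day is a weekend day with probability 1/2, which adds w²·s²/4. The inflation is w²·(1 - rho)/4. At an assumed rho of 0.7 this is 0.5, 1.9 and 7.5% for the three values of w.

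**Rolling 24-hour windows.** For noon injections, the Thu/Tue pair at 96 h is half weekend on both sides and cancels on clock time. The mean squared imbalance is (1 + 0 + 1)/3 = 2/3, so the inflation is w²/3: 2.1, 8.3 and 33%.

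**Five-day mean.** Weekend days in periods 1 and 2 are 2 and 1 for Wednesday starts, and 2 and 2 for Thursday and Friday starts, so the imbalances are 0.2, 0 and 0. With independent days (assumed) the inflation is (0.04/3)·w²/(2/5) = 0.033·w²: 0.2, 0.8 and 3.3%.

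**Procedure day.** At an exact 5-day gap, day 5 after injection 1 is the day of injection 2. If day 5 is dropped from both periods, the weekend counts are 2 and 0, 2 and 1, and 2 and 2; the imbalances are 0.5, 0.25 and 0; and the inflation is ((0.25 + 0.0625)/3)·w²/(2/4) = 0.208·w²: 1.3, 5.2 and 20.8%.

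**The case against.** A reader might infer that every participant compares a weekend day with a weekday at 96 h. That needs three things together: a gap of exactly 5 days, where the Visit 3 text allows fewer; procedures on weekdays only, which the documents do not state; and whole-calendar-day totals, which item 2 does not specify. The documents do not support it as a general statement.

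A reader might also infer a material loss of power for steps. The documents give no weekend effect, the trial was not powered for steps, and the larger inflation figures belong to a paired contrast that the Statistical Plan does not contain. Under the unpaired test, variation between people swamps the weekday swing. The larger defect there is the unpaired analysis of crossover data, and the weekday is a refinement on top of it.

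Item 2 speaks of average daily steps. If that is a five-day mean, most of the imbalance cancels. This is a fair reading, although five separate marks are listed and the cancellation relies on counting day 5, which after injection 1 can be a procedure day.

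The promised within-group comparisons could be meant as paired lidocaine-saline comparisons, but no paired test is specified for them and none has a calendar term.

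Finally, one weekend term cannot remove person-specific patterns, and the baseline days before Visit 2 may be few. Both objections stand. All of this limits the size of the point. None of it supplies the missing pairing or the missing day-type term.

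**Conclusion.** The point holds as a minor one. Matched step days never share a weekday at any gap of 5 days or fewer, and the plan for steps has neither a participant term nor a day-type term. The mismatch shares rest on the exact gap, on weekday procedures and on how a step day is defined. The variance figures rest on an assumed weekend effect.

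A reader might take this as bias in the lidocaine-saline contrast. With randomised order the expected contribution is zero; some imbalance could remain only by chance or if completers are unequal by sequence.

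The weekend term itself buys little. Most of the gain over a single-day contrast comes from pooling days within participant: with independent days, a five-day mean cuts the variance from 2s² to 2s²/5. The change is a modest, nearly free improvement to one secondary endpoint. The primary outcome and N = 20 are not affected.

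**What to change.** In the Statistical Plan, replace the unpaired test for steps with one mixed model of daily step totals containing:

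- a participant random effect;
- treatment;
- period, with the counter days before the first injection coded as their own untreated baseline period;
- day since injection;
- a weekend-versus-weekday indicator for the day counted.

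Define a step day (calendar day or 24-hour window) and state what average daily steps means. Exclude or flag procedure days. Report the lidocaine-saline difference with its 95% CI, and state that the weekend term removes the average weekend effect only.

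The Visit 2 and Visit 3 passages must be reconciled on the interval between injections. At a gap under 5 days, the 120 h mark after injection 1 falls after injection 2.

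Cost: SAP wording and a few model degrees of freedom. No new data are needed, and the analysis works with the visit schedule as it stands.
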